1. BACKGROUND

Spinal orthotics (braces) are effective in preventing curve progression in patients with adolescent idiopathic scoliosis. Braces work by providing corrective forces to relevant areas of the spine, but little is known about the amount of force required, or how forces change during activities and over time in response to changes in the shape of the patient's spine and torso. Therefore, it is important to be able to accurately measure these forces over the patient's course of treatment and to understand how much variation is normal, and when variation indicates that modifications need to be made to the brace in order to optimize its effectiveness.

The GSM engineering team has developed a smart pad sensor system capable of detecting changes in force magnitude and direction, but to date, the sensor system has only been evaluated on a test fixture. The smart pad sensor system of the GSM brace captures force data in two ways: interval and conditional. As the name implies, interval sampling captures sensor data at a consistent sampling rate. The objective of the conditional sampling is to capture force data when the patient and their brace are in a consistent state. This conditional sampling allows for a much more meaningful relative measure of brace performance. A conditional sample is triggered by the donning of a brace after the brace has been off the patient. Each interval force log includes the following data: 1) timestamp 2) voltage measurements for each of eight sensors embedded in the pad, and 3) readings from a 3-axis accelerometer. Each conditional force log includes the following data: 1) timestamp, 2) voltage measurements for each of the eight sensors, 3) readings from a 3-axis accelerometer, 4) the algorithmically determined force value (FV), and 5) the algorithmically determined X-Y coordinates for an equivalent point load. The smart pad system integrates with the standard sensor system placed in all braces and the data can either be stored and downloaded by the research team at study visits, or, if the subject is participating in the optional GSM Brace Wear Mobile App substudy, the data are uploaded to cloud storage when the subject syncs with the sensor.

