2. OBJECTIVE

The primary goal of this substudy is to validate the ability of a pressure-sensor equipped pad (GSM Smart Pad, smart pad) to accurately and reliably measure static and dynamic forces through a combination of lab and field testing using human subjects enrolled in the GSM Pilot study.

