3. PROTOCOL

Evidence for the accuracy and reliability of the force values generated by the smart pad system will be inferred via a series of comparisons to known forces and to a gold-standard measurement system (Tekscan pressure map/I-Scan™ system) both in the lab and in field testing with patient subjects. Analyses of repeated measures within each smart pad and between smart pads will be performed.

Lab Testing Materials and Methods

Lab Testing Phase 1. Twelve smart pads will be fabricated for testing and serialized in order to track performance over time. A benchtop test fixture will apply loads of 100N, 110N, 136N and 150N maintained for five minutes each with a 0-N dwell of 5 minutes in between loads. Loads will be applied in four rotational positions: neutral, 10-degree rotation from neutral, 20-degree rotation from neutral, and 30-degree rotation from neutral. Each of the 16 unique loading scenarios (magnitude x direction) will be run 10 times. The average force value under each of these conditions will be saved and analyzed. These 12 smart pads will then be used in field testing.

Lab Testing Phase 2. The smart pads removed from the brace at the 30-day follow-up visit will undergo repeat testing on the bench test fixture under the same 16 loading conditions.

Field Testing Materials and Methods

Subjects

Twelve subjects will be recruited from multiple sites to participate in the field testing. We will draw from the pool of patients who have consented to participate in the GSM Brace Pilot study. They will be told that participation in both studies is completely voluntary. Enrolled subjects may choose to stop participating at any time.

Visits and Procedures

Subjects in the substudy will undergo all procedures/assessments as those in the Pilot study. Participation in the substudy will last for approximately 1 month. One additional study visit will be required at approximately 1 month after Baseline. Otherwise, substudy procedures will

occur coincident with the Baseline, 1-week and 3-month follow-up visits in the Pilot protocol.

Baseline Visit. Subjects in the substudy will receive a GSM brace that includes one of the serialized smart pads tested during Lab Testing Phase I. No additional procedures or assessments for the substudy occur at this visit.

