Visit 2 (1-2 weeks after Baseline). Substudy procedures will add approximately 1 to 1.5 hours to the total duration of this study visit. The following procedures/assessments will take place in addition to the Pilot study activities (in-brace x-ray, safety check):

1. Calibration of the pressure map. The Tekscan pressure map is a very thin, flexible material embedded with force sensors to measure the magnitude and distribution of force exerted over an area. This map must be calibrated prior to use. To calibrate the map, the orthotist and research team will establish the area where the brace's thoracic pad would contact the subject's torso. The pressure map is then placed against the subject's torso with the smart pad (not yet attached to the brace) is centered over the map. A handheld force gauge (Mark 10 Series 4) is pressed on the smart pad to successively apply 80-N and 120-N forces to the patient for a period of less than 1 minute each. These known forces are then used by the I-Scan™ system to calibrate the pressure map for subsequent readings.
2. The smart pad is then placed in the GSM brace. The subject will don (put on) the brace, and the research team will place the pressure map between the subject's torso and the smart pad. The orthotist will assist the subject to adjust the strap tension and position of the brace. The subject is then asked to stand for 5 minutes in a normal posture with minimal spinal flexion or extension.
3. The subject will then be asked to doff (remove) the brace for 5 minutes.
4. Steps 2-3 are repeated for a total of four don-doff trials. During these trials, both the pressure map and the smart pad will capture force data. The smart pad will capture interval data once per minute; the don and doff trials will trigger the algorithm to capture one conditional sample for each trial.

Interim Between Visit 2 and the 1-Month Visit. The subject will continue to wear the GSM brace with the smart pad for a period of approximately 30 days. During this time, the smart pad will continuously capture data. These data will be stored on the device and transmitted to the cloud when the device is paired with the GSM mobile app (if the subject is also participating in the optional GSM Brace Wear Mobile App study). If the subject does not pair with the device during this period, the data will be retrieved by the research team at the 1-month visit.

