8. SAMPLE SIZE CALCULATIONS AND STATISTICAL ANALYSIS

No formal sample size/power calculations were done to arrive at the sample of 12 subjects. Given the large number of repeated measures data to be collected, and given the results from earlier bench work, we anticipate data from 12 subjects are adequate to attain the precision necessary to make informed decisions about the accuracy and reliability of the sensors in this study.

Lab Testing Analysis: The distribution of force values generated by each smart pad unit under each scenario will be characterized by the mean, standard deviation and coefficient of variation (CV, $((\text{mean}/\text{s.d}) * 100)$).

1. The inter- and intra-unit reliability of the force measures will be inferred by testing the variation of the means and the Csv within and between the 12 smart pad units under each of the 16 scenarios using the R package cvequality (Version 0.1.3; Marwick and Krishnamoorthy 2019) and repeated measures ANOVA. The quality control standard will be set at a CV of 5% or less. Units that demonstrate Csv >5% will not be used in the field testing.
2. Reproducibility/durability of smart pad measurements will be assessed using repeated measures ANOVA comparing Test 1 to Test 2 measures.

Field Testing Analysis

1. The force values measured by the I-Scan system and the smart pad during the Baseline and 1-Month visits will be compared using repeated measures analysis of variance.
2. The means and Csv of the force values over the 30-day wear period will be evaluated, looking for changes over time, and within and between Active and Rest periods using repeated measures ANOVA.
3. A regression model will be derived to convert each 24-hour set of force values to an estimate of the number of hours the brace was worn, using the temperature monitor output as the gold standard. The predictive accuracy of the smart pad model will be assessed using calibration plots and other error estimates.

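### The substudy's only in-patient check of smart-pad force against a reference names ANOVA but no agreement summary, and the 1-month text does not say which pad is measured

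*Combined protocol and SAP*

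**What the plan says.** All references are to Appendix 1.

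- **Goal (section 2).** The aim is to validate the pad's ability "to accurately and reliably measure static and dynamic forces", in the laboratory and in patients. Section 1 notes that so far "the sensor system has only been evaluated on a test fixture".
- **Reference (section 3).** The Tekscan/I-Scan pressure map is treated as the gold standard. Accuracy is also to be inferred from known loads on the bench.
- **Field comparison (section 8, Field item 1).** Pad and I-Scan force values "during the Baseline and 1-Month visits will be compared using repeated measures analysis of variance". No bias estimate, limits of agreement or other error measure is named. Field item 3 does plan calibration plots and error estimates, but for the wear-hours model.
- **Trials (section 3, Visit 2).** After the map is calibrated, the subject dons the brace, stands for 5 minutes and removes it for 5 minutes. "Steps 2-3 are repeated for a total of four don-doff trials". Both systems record throughout.
- **Pads (section 3).** Twelve pads are made and "serialized in order to track performance over time", one for each of 12 subjects. In Lab Phase 2, "The smart pads removed from the brace at the 30-day follow-up visit will undergo repeat testing on the bench test fixture".
- **1-Month Visit (section 3).** The text mentions removal of the pad for Phase II, then installation of a replacement, then repetition of the Visit 2 procedures. It does not say which pad is in the brace for those procedures.
- **Baseline (section 3).** "No additional procedures or assessments for the substudy occur at this visit".

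**The concern.** There are two separate problems.

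The first is the choice of statistic. Someone using the pad will rely on single readings, so accuracy in patients means knowing how far one pad reading may lie from the reference. A mean-difference test answers another question. It can be non-significant when readings scatter widely around I-Scan, and significant when they sit close to it with a small constant offset. Both systems record force in every trial, so nothing is lost if agreement is calculated later. As written, though, the plan does not commit to it.

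The second is the pad at 1 month. If sites swap pads before the repeated trials, the only in-patient reference check after about 30 days of wear is made on pads that were not worn, and for which no bench test or CV check is described. Every subject would then change pad between the two sessions, so a visit effect in item 1 could reflect time, wear or the new unit. This cannot be repaired at analysis. The substudy recruits from multiple sites, so practice could also differ between them.

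A smaller point is that item 1 names Baseline as a measurement session, while section 3 says no substudy procedures occur then.

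**Working it through.** **Is there a figure to reproduce?** No. Section 8 states that the 12 subjects were not chosen by a power calculation, and gives no alpha, SD or agreement limit for force. The calculations below assume a two-sided alpha of 0.05, are scale-free where possible, and are illustrations.

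**1. Trial counts.** 12 subjects × 4 don-doff trials = 48 trials per visit, or 96 over two visits. Each trial triggers one conditional sample, the log type for which section 1 lists a force value. So 48 is also the minimum number of paired force values per visit. Interval logs, taken once a minute, hold the sensor voltages and may supply more.

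**2. What the ANOVA device test responds to.** With two devices and balanced data, the device effect is equivalent to a paired t-test on the 12 subject-mean differences: df = 11, critical t = 2.201, noncentrality = (bias/SD) × √12. Holding the bias fixed and increasing the SD of those differences:

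| SD of differences | bias/SD | Noncentrality | Power |
|---|---|---|---|
| ×1 | 1.00 | 3.464 | 88% |
| ×2 | 0.50 | 1.732 | 35% |
| ×4 | 0.25 | 0.866 | 12% |

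With zero bias the test is non-significant in about 95% of studies at any spread (simulated rejection 0.051, 0.050 and 0.048), while the limits of agreement widen ×1, ×2, ×4. These are properties of any paired comparison with 12 subjects, not estimates for this pad.

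**3. Same point with assumed newton values.** True 95% limits = bias ± 1.96 × √(between-subject variance + within-subject variance). Rejection rates come from 20,000 simulated studies of 12 subjects × 4 trials. All SDs and biases are assumptions.

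- Bias 0, SDs 20 and 5: √(400 + 25) = 20.6, limits about −40 to +40 N. The ANOVA rejects in 4.9%.
- Bias 2, SDs 1 and 1: √2 = 1.41, limits about −0.8 to +4.8 N. The ANOVA rejects in about 100%.

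The case with poor agreement is rarely flagged and the case with close agreement nearly always is.

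**4. Is an agreement summary feasible with 12 subjects?** Treating 12 differences as independent, the 95% CI half-width is 2.201/√12 = 0.64 SD for the bias. For each limit it is 2.201 × √(1/12 + 1.96²/22) = 2.201 × 0.508 = 1.12 SD. That is imprecise, but it can be estimated and reported.

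**5. Which pad at 1 month?**

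| Order of steps | 1-month trials on worn serialized pads | Subjects changing pad between sessions |
|---|---|---|
| As listed: remove, replace, repeat procedures | 0 of 48 | 12 of 12 |
| Procedures first, then swap | 48 of 48 | 0 of 12 |

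The text permits either.

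**6. Which first session?** Section 3 lists Baseline among the visits with substudy procedures and then says none occur there. Section 6 mentions a longer Visit 1. Section 8 names Baseline. The detailed calibration and don-doff procedures are set out under Visit 2, which points to Visit 2 as the first paired session.

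**The case against.** The plan never says that a non-significant ANOVA will be read as agreement. A reader might infer that rule, but section 8 speaks only of precision for informed decisions, so the power figures show what the test can and cannot do and not how the sponsor will use it. Repeated-measures ANOVA also yields a mean difference and variance components from which limits could be built. That stands, and it makes the first part a reporting gap that can be closed at analysis. The gap remains, because nothing commits the sponsor to an agreement summary for force.

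A reader might also infer that the validation has no accuracy or durability evidence without item 1. The documents do not support this. The bench work applies known loads in 16 scenarios, 10 runs each, with means, SDs and a 5% CV standard. Worn pads are retested in Lab Phase 2, and Field item 2 follows force values over the 30 days. None of these compares pad force with a reference on a patient.

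On pad order, it would be too strong to say that replacement pads will be measured. The listed order suggests it, but no sequence is stated. Nor is 48 a firm total of force values: section 8 uses that term for active and rest periods and for 24-hour sets, so interval data may add pairs.

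Finally, this is an optional substudy of a descriptive pilot. That limits the weight of the point, but Appendix 1 is framed as a clinical validation and plans inferential analyses of its own.

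**Conclusion.** The point holds and should be fixed. Item 1 is the only in-patient comparison of pad force with a reference, and the method it names does not measure agreement of individual readings, which the accuracy goal needs. This part costs no data. No size in newtons can be given, because the documents report no SD for pad-minus-I-Scan differences.

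The pad-order part is conditional but irreversible: 0 of 48 one-month trials on worn serialized pads if the listed order is followed, with visit and pad inseparable, against 48 of 48 if the trials come first. These counts assume that all 12 subjects complete both sessions.

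The mention of Baseline is an internal inconsistency. A reader might treat it as a simple slip for Visit 2, and that is the likelier reading, but the passages conflict and the sponsor must reconcile them.

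Visit 2 readings, the bench analyses, Field item 2 and the pilot's primary aims are unaffected.

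**What to change.** 1. **Field item 1.** Alongside the ANOVA, report mean bias (pad minus I-Scan) with its 95% CI and 95% limits of agreement for repeated measures, separately by visit, from a model with between-subject and within-subject variance components. This uses data already being collected and costs a sentence or two.
2. **1-Month Visit text.** State that calibration and the four don-doff trials are run with the original serialized pad, before it is removed for Phase 2 bench testing and the replacement is installed. Record the pad serial number with each field reading. The cost is the order of steps at an existing visit and one data field, with no extra visit, device or reading.
3. **Editorial.** Reconcile Baseline in item 1 with the visit list, the Baseline and Visit 2 descriptions in section 3, and the reference to a longer Visit 1 in section 6, so that the first paired session is named consistently.

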Appendix 1.

Green Sun Medical Pressure-Sensor Equipped Pad Clinical Validation

Substudy of the Pilot Trial Green Sun Medical Dynamic Brace

Protocol Version 1.0

14 Jan 2021

Substudy participation is optional for subjects newly enrolled in the Pilot trial. Twelve subjects at select participating sites will be enrolled.

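### Substudy Field item 2: an under-specified repeated measures ANOVA on 12 subjects should give way to subject-level slopes with an interval, and the number of readings should not justify the sample size

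*Combined protocol and SAP*

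**What the plan says.** Appendix 1 fixes the size of the substudy: "Twelve subjects at select participating sites will be enrolled". Section 8 of the appendix adds: "No formal sample size/power calculations were done to arrive at the sample of 12 subjects". It gives two reasons for accepting 12, "Given the large number of repeated measures data to be collected, and given the results from earlier bench work", and on that basis calls the data "adequate to attain the precision necessary to make informed decisions about the accuracy and reliability of the sensors in this study". No target precision, interval width or agreement limit accompanies the statement.

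Field Testing item 2 reads "The means and Csv of the force values over the 30-day wear period will be evaluated", followed by "looking for changes over time, and within and between Active and Rest periods using repeated measures ANOVA". It does not say what one level of time is, which covariance or sphericity handling applies, what significance level is used, or what happens to days without data. Active and Rest periods are not defined anywhere. A 24-hour unit appears only in item 3, the wear-time regression.

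**The concern.** Classical repeated measures ANOVA compares the means of a set of time levels. It assumes sphericity and, in its textbook form, a value for every subject at every level. Continuous force recording on a worn brace yields a long series per subject, in which neighbouring values are likely to be alike and some may be missing. With many levels and 12 subjects, the result can then depend on choices the plan leaves open.

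Two further problems do not depend on those choices. An omnibus test over time says only whether the level means differ; it does not say by how much recorded force changes or how precisely that is known. The sample size paragraph also treats many readings as a source of precision, although the scatter between subjects and between pads is learned from 12 of each.

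At stake is how the substudy describes force over time. The appendix's Background wants to know how much variation is normal and when variation signals that the brace needs modifying. That calls for an estimate with an interval.

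**Working it through.** **1. The plan's own figure.** The number 12 cannot be reproduced. No calculation was done, and no significance level, power, SD, correlation or precision target is given.

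**2. Inputs.**
- From the documents: n = 12 subjects, each wearing one serialized smart pad; repeated measures ANOVA; a wear period of about 30 days between Visit 2 and the 1-Month visit (Appendix 1, section 3). The same section also puts the 1-Month visit about one month after Baseline and Visit 2 at 1-2 weeks after Baseline. That leaves 30 - 14 = 16 to 30 - 7 = 23 days. The number of possible daily levels is therefore itself unclear, and these statements must be reconciled.
- Assumed: two-sided 5% level; first-order autoregressive errors with correlation up to 0.9 between adjacent levels; days missing independently at 1-10%.

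**3. Type I error.** Data were simulated with no true mean change, 4,000 sets per case. The ANOVA statistic is F = MS(time) / MS(time x subject) on k - 1 and 11(k - 1) degrees of freedom, for k time levels. It was judged uncorrected and with the Greenhouse-Geisser correction. The comparator is one slope per subject followed by a one-sample t test on 11 df.

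| Levels k | Correlation | Uncorrected | Greenhouse-Geisser | Per-subject slope |
|---|---|---|---|---|
| 4 | 0.5 | 5.8% | 4.1% | 5.0% |
| 4 | 0.7 | 7.0% | 4.7% | 5.1% |
| 4 | 0.9 | 7.0% | 4.7% | 4.9% |
| 20 | 0.5 | 9.0% | 1.3% | 4.4% |
| 20 | 0.7 | 12.4% | 3.3% | 5.8% |
| 20 | 0.9 | 15.3% | 3.5% | 4.8% |
| 30 | 0.5 | 9.0% | 0.7% | 4.8% |
| 30 | 0.7 | 12.7% | 1.3% | 5.0% |
| 30 | 0.9 | 18.6% | 3.3% | 5.2% |

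Monte Carlo error at 5% is 1.96 x sqrt(0.05 x 0.95 / 4000) = 0.7 percentage points. At 30 levels the uncorrected rate is 5.4% with correlation 0 and 6.7% with 0.3. A separate simulation over 16-30 levels (3,000 sets per case) gave uncorrected rates of 8.4-8.8%, 11.0-13.7% and 14.1-18.9% at correlations 0.5, 0.7 and 0.9. Hence the range of about 8-19%.

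**4. Gaps, if only complete subjects are used.** The expected number complete is 12 x (1 - p)^k.
- 30 days: p = 1% gives 12 x 0.740 = 8.9; 2% gives 12 x 0.545 = 6.5; 5% gives 12 x 0.215 = 2.6; 10% gives 12 x 0.042 = 0.5.
- 20 days: 1%, 2% and 5% give 9.8, 8.0 and 4.3.

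With per-subject slopes and 5-10% of days missing at random (30 days, correlation 0.5), all 12 subjects stay in and type I error is 4.9-5.2%.

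**5. Precision with 12 units.** For a mean change estimated from one value per subject, the 95% CI half-width is t(0.975, 11) / sqrt(12) = 2.201 / 3.464 = 0.64 times the between-subject SD of that change. More readings shrink only the within-subject part of that SD; the true variation between subjects is still averaged over 12. For a between-pad SD, the 95% limits are sqrt(11 / chi-square) times the estimate: 0.71 and 1.70. That holds however many readings each pad gives.

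**The case against.** The strongest reply is that this is one exploratory item in an optional substudy of a pilot, with no decision tied to its p-value. Section 8.4 of the main protocol plans no formal hypothesis testing for the pilot. That stands, and it sets the severity.

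Several stronger readings are tempting, and the documents do not support them:

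- **That false signals are likely.** Item 2 specifies neither daily levels nor an uncorrected test. Even at 30 levels and correlation 0.9, more than 80% of null analyses would show nothing. Weekly levels are near nominal, and the Greenhouse-Geisser version errs the other way.
- **That subjects with gaps will be dropped.** No complete-case rule is written. The sensor board holds more than 60 days of data (main protocol, section 1.3), and data not synced are retrieved at the 1-Month visit. Subjects do exchange and recharge the battery themselves, and they may withdraw, so gaps are possible; no rate is documented.
- **That item 2 tests sensor drift.** It has no reference force. Drift is addressed by the bench re-test at known loads (Lab Testing Phase 2) and the I-Scan comparison (Field item 1). A change seen during wear mixes sensor, brace and patient.
- **That the ANOVA counts readings as independent.** It has a subject term, and for within-subject contrasts a shared subject level cancels. The criticism of repeated readings belongs to the sample size paragraph. That paragraph also cites bench work, which can inform variation under fixed loads but not how force changes between wearers.

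A fair technical reply is that the simulated comparator was the per-subject slope, not the mixed model proposed below. That is why the fix asks for small-sample degrees of freedom and keeps the slope summary as a fallback.

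**Conclusion.** The point holds in a limited form. Item 2 leaves open the choices that decide how its test behaves. With many serially correlated levels, the uncorrected route is too liberal (about 8-19%) and the Greenhouse-Geisser route too conservative (about 1-4%). A complete-case rule could leave few subjects. With about four weekly levels, error control is acceptable. These rates rest on an assumed autoregressive correlation of 0.5-0.9, a two-sided 5% level and assumed independent missing days; none comes from the documents.

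Two parts need none of the correlation or missing-day assumptions. The omnibus test gives no size of change with an interval, whatever the time unit. The number of readings is not a sound ground for saying that 12 subjects are precise enough. Severity is low.

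**What to change.** **Item 2.** Replace the ANOVA with a linear mixed model for recorded force: random intercept and slope per subject, Active/Rest as a fixed effect, serially correlated errors and small-sample degrees of freedom. If the model does not converge, use one slope per subject and a t interval. Use all available days and keep subjects with gaps. Report change in N per week with a 95% CI. State the time unit and the length of the wear period, define Active and Rest, and give the CVs a corresponding estimate with an interval.

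**Label.** Call the result change in recorded brace force. Leave sensor drift to the bench re-test and the I-Scan comparison.

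**Sample size paragraph.** Remove the number of repeated readings as grounds for adequacy. State what 12 subjects or pads deliver: a 95% CI half-width of about 0.64 between-subject SD for a mean change, and a between-pad SD known to within 0.71-1.70 times its estimate.

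**Cost.** A change of wording in section 8 of the appendix, standard software and slightly more analysis work. No extra subjects, visits or measurements are needed. The stated precision becomes less favourable.
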